1. PROTOCOL SUMMARY

1.1. Summary of Trial Design

Title:	A phase II study of ni volumab m onotherapy in patients with relapsed/refractory Hodgkin lymphoma, fit for a utologous stem cell transplantation, who fail to reach complete metabolic remission after first or second line salvage therapy
Short Title/acronym:	ANIMATE
EUDRACT no:	2017-002544-32
Sponsor name & reference:	University College London (UCL/15/0515)
Funder name & reference:	Bristol-Myers Squibb (CA-209-445)
Clinicaltrials.gov no:	NCT03337919
Design:	Single-arm, open label, multicentre phase II trial
Overall aim:	To assess the efficacy of nivolumab as a second or third line salvage therapy in relapsed/refractory classical Hodgkin lymphoma patients, particularly as a bridge to stem cell transplant
Primary endpoint:	Overall response rate (ORR) by PET-CT scan following 4-8 cycles of nivolumab
Secondary endpoints:	 Progression-free survival at 1 year Overall survival at 1 year Proportion of patients proceeding to SCT (autologous or allogeneic) Safety & toxicity of nivolumab, particularly autoimmune toxicity OS and PFS stratified by partial metabolic response (PMR) versus complete metabolic response (CMR) on FDG-PET Transplant-related mortality and rate of serious complications of allogeneic transplant (grade 3-4 graft-vs-host disease, hyperacute graft-vs-host disease and steroid-responsive febrile syndrome)
Exploratory biological endpoints	 Correlate PET positive disease with histological evidence of disease on biopsy to establish biopsy negative PMR rate (subject to patient consent) Correlate disease response, as assessed by FDG-PET and histology, with serological markers, including serum TARC Evaluate the correlation between response to nivolumab and biological parameters e.g. PDL1 expression on Reed-Sternberg cells

[figure not shown]
Target accrual:	120 registered, to treat 30 patients		

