6.2.3. Inclusion criteria for trial treatment

- 1. Has received 2 cycles of first or second line salvage chemotherapy, (4 cycles if receiving treatment with brentuximab vedotin)
- 2. PET positive (Deauville score 4 or 5) after 2 cycles of first or second line salvage chemotherapy (4 cycles if receiving treatment with brentuximab vedotin)
- 3. Fit for further salvage chemotherapy
- 4. ECOG performance status 0-1
- 5. Creatinine clearance >30ml/min calculated by Cockcroft-Gault formula
- 6. Bilirubin <1.5 x ULN, ALT/AST <2.5 x ULN
- 7. Adequate bone marrow function (Hb >80g/l, Platelets >50 x 10⁹/l, neutrophils >1.0 x 10⁹/l)

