8.2. Treatment Summary

Patients for whom eligibility for treatment is confirmed (see section 7.2 for details) will receive 4-8 x 14-day cycles of nivolumab. Nivolumab 240mg will be administered on day 1 of each 14 day cycle. Dose banding is not permitted.

Trial treatment should begin within 4 weeks following the PET-CT scan to confirm eligibility for trial treatment (PET0).

	1	2	3	4	5	6	7	8	9	10	11	12	13	14
Nivolumab 240mg IV	Х													

Patients will have a PET-CT scan after 4 cycles (PET4). This should be performed on cycle 4, day 11-13 to allow time for central review before the cycle 5 day 1 visit would be due. Please note that patients must not proceed to cycle 5 prior to receipt of the PET4 central review report.

- If PET-negative (Deauville 1-3), they will stop nivolumab. Further management will be at the discretion of the treating clinician and the patient will be followed up as per the trial protocol (see section 9.6.2).
- If the scan shows disease progression, they will stop nivolumab and have further salvage at their treating clinician's discretion. They will enter into annual follow up for the trial.
- If the scan is positive (Deauville 4-5) but there is no evidence of disease progression, the patient will have a further 4 cycles of nivolumab. Following this, they will be followed up as per the trial protocol (see section 9.6.2).

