8.4. Dose Modifications

Dose reductions and escalations of nivolumab are **not** permitted. Nivolumab should be delayed for up to 4 weeks for the following:

- Any ≥ grade 3 Haematological toxicity (Hb <80g/dl, platelets <50 x10⁹/l, neutrophils <1.0 x10⁹/l)
- Any ≥ grade 3 drug-related, non–haematological AE **except**:
 - o Fatigue
 - o Alopecia
 - Drug related endocrinopathies adequately controlled with physiologic hormone replacement.
 - Electrolyte disturbances that can be corrected and are unlikely to cause clinical safety concerns.
- Any grade 2 auto-immune complication including pneumonitis, renal dysfunction, diarrhoea/ colitis, neurological complication, derangement of liver function tests. Guidelines for management of auto-immune complications are set out in Section 8.5.
- Any non-drug related AE where the in the local investigator's opinion delaying treatment is in the patient's best interest.

Treatment may be resumed once AEs resolve to grade ≤1 or baseline value. If the criterion to resume treatment is met (see section 8.5), the subject should restart treatment at the next scheduled time-point, as set out in the protocol. If treatment is delayed by >4 weeks, the subject should be permanently discontinued from study therapy. Treatment may be discontinued earlier at the discretion of the investigator if it is felt that continuing on the trial treatment will compromise a successful outcome for the patient.

A treatment summary form must be completed and sent to UCL CTC promptly if treatment is discontinued. The patient will enter follow up as per the trial protocol (see section 9.6.2).

Treatment Discontinuation Criteria

Nivolumab treatment should be permanently discontinued for the following:

 ≥grade 2 drug-related uveitis or eye pain or blurred vision that does not respond to topical therapy. Uveitis is inflammation of the eye, and includes anterior uveitis (synonymous with iritis), posterior uveitis (comprising vitritis, choriditis, retinitis, chroioretinitis) and pan-uveitis (inflammation of the anterior chamber, vitreous, retina and choroid).

- ≥grade 3 pneumonitis
- Any grade 4 drug related AE or laboratory abnormality apart from the following:
 - Grade 4 neutropenia <7 days (G-CSF may be instituted, and continued until neutrophils exceed 1.5x10⁹/L, as per institutional policy)
 - Grade 4 amylase or lipase abnormalities that are not associated with clinical symptoms

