9.3. Assessments prior to cycle 1 of Nivolumab

The following investigations are to be performed within 24 hours prior to starting Nivolumab:

Pregnancy test (urine or serum; WOCBP only)

The following investigations are to be performed within 3 days prior to starting Nivolumab:

- Clinical examination, including documentation of baseline adverse events
- Full blood count with differential*
- Biochemistry (ALT/AST, total bilirubin, alkaline phosphatase, urea, creatinine, calcium, magnesium, sodium, potassium, LDH, albumin, urate, glucose) *
- Thyroid function tests (TSH & Free T4; Free T3 to be performed if TSH/Free T4 abnormal)
- Test for autoimmune conditions (Amylase, lipase, ACTH)
- Blood samples to be taken and sent to the central laboratory at the Weatherall Institute of Molecular Medicine, Oxford (see section 10.2 and Laboratory Manual for details)

The following investigations must be carried out on the day of nivolumab administration:

Oxygen saturation measured by pulse oximetry at rest

^{1 =} PET CT to be performed 18 days after last administration of salvage treatment ±3 days

^{2 =} FBC and biochemistry must be performed at least 3 weeks after after last administration of cycle 2 salvage treatment (or cycle 4 of brentuximab vedotin) to allow time for count recovery. For WOCBP, a pregnancy test is required within 24 hours prior to starting nivolumab.

^{*} Do not need to be repeated if investigations for confirmation of eligibility (see section 9.2) were performed within 3 days prior to starting Nivolumab

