9.4. Assessments during Treatment

During treatment the patient should be seen every 2 weeks and the following assessments performed within 3 days prior to the start of each cycle:

- Clinical examination
- Full blood count with differential
- Biochemistry (ALT/AST, total bilirubin, alkaline phosphatase, urea, creatinine, calcium, magnesium, sodium, potassium, LDH, albumin, urate, glucose)
- Tests for autoimmune conditions (amylase, lipase, ACTH)
- Cycles 3, 5 & 7: pregnancy test (urine or serum; WOCBP only)
- Cycle 4 and cycle 7: Thyroid function tests (TSH & Free T4; Free T3 to be performed if TSH/Free T4 abnormal)
- Adverse event assessment

The following investigations must be carried out on the day of nivolumab administration:

Oxygen saturation measured by pulse oximetry at rest

Blood samples for translational research

Blood samples are to be taken and sent to the central laboratory at the Weatherall Institute
of Molecular Medicine, Oxford within 3 days prior to the start of cycles 2, 4, 6 and 8, and
at the 1 month post-treatment visit (see section 10.2 and Laboratory Manual for more
details)

Scanning required after cycle 4

- PET-CT scan to be carried out on cycle 4, day 11-13 as per trial requirements on an approved scanner, and images sent to the PET core lab for central review (PET4; see trial Imaging Manual for details).
- Contrast enhanced CT scan (ceCT). If feasible, this should be performed at the same imaging session as the PET-CT. If performed at the same session, the ceCT scan should be performed after the low dose PET-CT (see trial Imaging Manual for details).

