12.2. Reporting Procedures

Adverse Event Term

An adverse event term must be provided for each adverse event. Wherever possible a valid term listed in the Common Terminology Criteria for Adverse Events (CTCAE) v5.0 should be used. This is available online at:

http://evs.nci.nih.gov/ftp1/CTCAE/

Severity grade

Severity grade of each adverse event must be determined by using CTCAE v5.0. This is available online at:

http://evs.nci.nih.gov/ftp1/CTCAE/

Causality

The relationship between the treatment and an adverse event will be assessed.

For AEs, the local PI or designee will assess whether the event is causally related to trial treatment.

For SAEs, a review will also be carried out by the Sponsor's delegate.

Causal relationship to each trial treatment must be determined as follows:

- Related (reasonable possibility) to a trial treatment
- Not related (no reasonable possibility) to a trial treatment

UCL CTC will consider events evaluated as related to be adverse reactions.

Responsibility for reporting safety events following transfer of care

In the event of transfer between trial sites

UCL CTC must be informed if a patient's care is transferred to another trial site (see section 15.4 – Transfer of Care). The trial site caring for the patient at the time of awareness of AE, SAE, AESI, Urgent Event onset or pregnancy is responsible for completing and sending relevant reports to UCL CTC. When the patient's care is transferred, the referring site must provide sufficient information about the patient's trial participation (i.e. a copy of the patient's completed CRFs up to the date of transfer) to the new site to allow them to complete SAE reports.

In the event of transfer between a trial site and a non-trial site

The trial site will remain responsible for completing and sending AE, SAE, AESI Urgent Event and pregnancy reports to UCL CTC. If a patient is discharged to the care of a non-trial site, the Pl/study team at the trial site should ensure that they are sent regular updates on the patient's progress and notified of any admissions or significant medical developments (including relapses and deaths), in order that the site's reporting responsibilities can be fulfilled.

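### Section 8.4 prints the haemoglobin limit for delaying nivolumab in g/dl instead of g/l, a tenfold unit misprint in a dosing rule (minor)

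*Protocol*

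**What the plan says.** Section 8.4 of the protocol (Dose Modifications) lists the circumstances in which nivolumab is to be held for up to 4 weeks. The haematological entry begins "Any ≥ grade 3 Haematological toxicity (Hb <80g/dl" and continues with "platelets <50 x10⁹/l, neutrophils <1.0 x10⁹/l". A hold lasting longer than 4 weeks leads to permanent discontinuation.

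The criteria for starting trial treatment, in section 6.2.3 and again in the summary in section 1.1, cover the same three blood counts. There the haemoglobin entry reads "Adequate bone marrow function (Hb >80g/l", followed by platelets above 50 x 10⁹/l and neutrophils above 1.0 x 10⁹/l.

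On grading, section 12.2 states: "Severity grade of each adverse event must be determined by using CTCAE v5.0". The protocol does not reproduce the CTCAE haemoglobin cut-offs.

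**The concern.** The limit in section 8.4 is a decision threshold that sites apply while patients are on treatment. As printed, it lies far above any haemoglobin a patient can have, so the number cannot separate patients who need a delay from those who do not. It is also out of line with the haemoglobin limit the protocol gives elsewhere, although the two companion limits match exactly.

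At stake is the clarity of a safety rule whose further consequence is permanent discontinuation. Section 14.1 also has central monitoring look for signs that dose modification rules were not followed, and a check against the printed haemoglobin number would be meaningless. No statistical quantity depends on it.

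**Working it through.** **Inputs**

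| Analyte | Delay limit (8.4) | Eligibility limit (6.2.3 and 1.1) |
|---|---|---|
| Haemoglobin | below 80 g/dl | above 80 g/l |
| Platelets | below 50 x 10⁹/l | above 50 x 10⁹/l |
| Neutrophils | below 1.0 x 10⁹/l | above 1.0 x 10⁹/l |

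**Unit conversion.** One litre is 10 dl, so 80 g/dl x 10 dl/l = 800 g/l.

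**Ratio of delay limit to eligibility limit**

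- Haemoglobin: 800 / 80 = 10
- Platelets: 50 / 50 = 1
- Neutrophils: 1.0 / 1.0 = 1

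Only haemoglobin departs from 1, and it does so by exactly the factor that separates g/dl from g/l. The numeral 80 is the same in all three sections.

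**Is the correction unambiguous?** There are two ways to repair the entry. Changing the unit gives 80 g/l. Keeping g/dl and moving the decimal gives 8.0 g/dl, and 8.0 x 10 = 80 g/l. Both lead to the same limit.

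**How often the line is consulted.** Section 1.1 plans "120 registered, to treat 30 patients", and section 8.2 says eligible patients "will receive 4-8 x 14-day cycles of nivolumab". Section 9.4 has "the following assessments performed within 3 days prior to the start of each cycle", and these include a full blood count. The count before cycle 1 falls under section 9.3 and precedes any nivolumab, so it is left out.

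- All 30 patients complete 4 cycles: 30 x (4 − 1) = 90 counts
- All 30 patients complete 8 cycles: 30 x (8 − 1) = 210 counts

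This range shows how often the rule is used under planned treatment. It is not a number of wrong decisions, and it is not a strict bound. Early stopping lowers it, while replacement of patients found ineligible after starting (section 18.1) and repeat counts during a delay could raise it.

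**The case against.** The strongest reply is that the misprint reveals itself. Nobody has a haemoglobin near 80 g/dl, the intended figure appears in sections 6.2.3 and 1.1, and any haematologist will read it as 80 g/l. The operative words are also grade 3 or worse, with the bracket only explaining them. A patient with a normal haemoglobin has no grade 3 toxicity, so the rule as a whole does not capture everyone; only the number in the bracket does. Both points stand, and they are why the matter is minor. They do not make the printed limit correct.

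A second reply is that eligibility and delay limits serve different purposes and may properly differ. That is true in general. Here, however, the platelet and neutrophil limits coincide across the sections, the haemoglobin numeral coincides too, and 800 g/l is impossible under any purpose.

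A third is that the CTCAE fallback cannot be checked from the protocol, because its haemoglobin cut-off is not printed there. This is fair. The correction therefore rests on the agreement with sections 6.2.3 and 1.1; the grading requirement shows only that sites have another route to a cut-off.

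Finally, a fault in reading the PDF is unlikely. It would have had to add a letter to one unit while leaving the litre unit intact in the other two limits of the same bracket. No other part of the protocol corrects or explains the unit.

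**Conclusion.** The concern holds, at minor severity. Section 8.4 states the haemoglobin limit for delaying nivolumab ten times too high (800 g/l against 80 g/l), because the unit is wrong. The conclusion assumes that the delay limit was meant to mirror the eligibility limit, as the platelet and neutrophil limits do.

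The likely practical effect is slight. A usable criterion survives in the grade 3 wording, and a literal reading would withhold drug rather than dose a patient who should be delayed. Nothing in the sample size, the primary endpoint or the analysis changes.

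**What to change.** In section 8.4, change the haemoglobin limit to below 80 g/l (or, equivalently, below 8.0 g/dl) at the next protocol amendment, and tell sites about the correction. Using g/l keeps the unit consistent with sections 6.2.3 and 1.1. The cost is a one-unit text change and a short note to sites.

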8.5. Management of Adverse Events

8.5.1. Autoimmune complications

Because of its mechanism of action, autoimmune complications are common with nivolumab. Where sites have local policies for management of autoimmune toxicity, these may be followed. Where there is no local policy, suggested guidelines for management of such autoimmune complications are set out below. Clinicians are also advised to refer to the manufacturer's guidelines (see summary of product characteristics).

Autoimmune toxicities are regarded as AEs of special interest for this trial, requiring expedited reporting to UCL CTC. Please refer to section 12.4 for details of how and when to report autoimmune events.

If treatment is delayed by >4 weeks due to autoimmune toxicity, the subject should be permanently discontinued from study treatment.

8.5.1.1 Management of auto-immune diarrhoea/colitis

Exclude infective and disease-related causes e.g. with stool culture and gastrointestinal endoscopy if indicated.

Diarrhoea/ Colitis CTCAE v5 grade	Action – trial treatment	Recommended management of toxicity
Grade 1 Diarrhoea <4 stools/day over baseline	Continue nivolumab at 240mg	Treat symptoms as per local policies e.g. Loperamide If worsens: Treat as below, as per severity
Grade 2 Diarrhoea 4-6 stools/day over baseline	Delay nivolumab treatment Restart nivolmab at 240mg if/when improves to grade 0.	Treat symptoms as per local policies.

IV fluids <24 hours Colitis: abdominal pain, blood in stool	If steroids given, patient must have been weaned to ≤10mg per day (or equivalent) before restarting treatment. Maximum permitted delay 4 weeks.	Consider investigation with lower GI endoscopy Consider prophylactic antibiotics. If symptoms persist >5-7 days or recur: Initiate steroid treatment as per local policy (recommended dose 0.5-1.0mg/kg/day IV methylprednisolone or equivalent dose of oral steroids). When symptoms improve to G1, taper steroids over at least 4 weeks. If worsens/ persists after 3-5 days on steroids: treat as G3-4.
Grade 3 and 4 Diarrhoea: G3: >7 stools/day over baseline; hospitalisation indicated; limiting self care ADL G4: life threatening consequences; urgent intervention indicated. Colitis: G3: severe adominal pain; peritoneal signs G4: life threatening; urgent intervention indicated (e.g. perforation)	Permanently discontinue nivolumab treatment.	Steroid treatment as per local policy (recommended 1-2mg/kg/day IV methylprednisolone or equivalent dose of oral steroids). When symptoms improve to G1, taper steroids over at least 4 weeks. Consider lower GI endoscopy. Prophylactic antibiotics for infection. If persists >3-5 days: refer to manufacturer's recommendations or manage as per local policy.

8.5.1.2 Management of autoimmune pneumonitis

Exclude infectious and disease-related aetiologies.

CTCAE v5 grade of pneumonitis	Action – trial treatment	Recommended management of toxicity
Grade 1 Asymptomatic, radiographic changes only	Continue nivolumab at 240mg.	Monitor for symptoms every 2-3 days. Re-image at least every 2 weeks Monitor closely for worsening of symptoms and treat as G2/G3 and G4 accordingly
Grade 2 Mild to moderate new symptoms; medical intervention indicated; limiting instrumental ADL	Delay nivolumab treatment. Restart nivolumab at 240mg if/when symptoms and radiographic appearances resove.	Monitor symptoms daily and consider hospitalisation. Steroid treatment as per local policy (recommended dose 1mg/kg/day IV methyl-

	If steroids given, patient must have been weaned to ≤10mg per day (or equivalent) before restarting treatment. Maximum permitted delay 4 weeks.	prednisolone or equivalent dose of oral steroids). Consider bronchoscopy. Prophylactic antibiotics. Infectious disease and respiratory referrals. Re-image every 1-3 days If improves: when symptoms resolve, taper steroids over at least 4 weeks. If not improving after 2 weeks
		or worsening: treat as G3-4
Grade 3-4: G3: Severe new symptoms New/worsening hypoxia Limiting self-care ADL Oxygen indicated G4: Life threatening respiratory compromise Urgent intervention indicated (e.g. tracheotomy or intubation	Permanently discontinue nivolumab treatment.	Hospitalise patient. Steroid treatment as per local policy (recommended dose 2-4mg/kg/day IV methylprednisolone or equivalent dose of oral steroids). Prophylactic antibiotics. Consider bronchoscopy. Infectious disease and respiratory referrals. If improves to baseline: taper steroids over at least 6 weeks. If not improving after 48 hours or worsening: manage as per local policy – consider additional immunosuppression e.g. infliximab, cyclophosphamide,

8.5.1.3 Management of autoimmune hepatitis

Exclude infective and disease related causes, and hepatotoxicity of other concomitant medications

Hepatitis CTCAE v5 grade	Action – trial treatment	Recommended management of toxicity
Grade 1: AST or ALT >ULN - 3xULN and/or Bilirubin >ULN - 1.5xULN	Continue nivolumab treatment at 240mg.	Continue monitoring of liver function tests as per protocol. If worsening, treat as G2 or G3-4
Grade 2: AST/ALT >3xULN - 5xULN and/or	Delay nivolumab treatment	Increase frequency of monitoring to every 3 days If persists >3 days or worsens:

Bilirubin >1.5xULN - 3xULN	Restart nivolumab at 240mg if/when results improve to baseline. If steroids given, patient must have been weaned to ≤10mg per day (or equivalent) before restarting treatment. Maximum permitted delay 4 weeks.	Steroid treatment as per local policy (recommended dose 0.5-1mg/kg/day IV methylprednisolone or equivalent dose of any oral steroids). If no improvement after a further 3 days, treat as for G3-4. Consider prophylactic antibiotics for opportunistic infections.
Grade 3-4: AST or ALT >5xULN and /or Bilirubin >3xULN	Permanently discontinue nivolumab treatment.	Increase frequency of monitoring to every 1-2 days: Steroid treatment as per local policy (recommended dose 1-2mg/kg/day IV methylprednisolone or equivalent dose of oral steroids). Add prophylactic antibiotics for
		opportunistic infections. Consult gastroenterologist.
		If returns to G2:
		taper steroids over at least 4 weeks
		If not improving after 3-5 days or rebounds:
		give additional immunosuppression as per local policy.

8.5.1.4 Management of autoimmune dermatitis

New or worsening rash. Exclude other non-autoimmune causes e.g. swab potentially infective lesions.

Rash CTCAE v5 grade	Action – trial treatment	Recommended management of toxicity
Grade 1-2:	Continue nivolumab treatment at	Treat symptoms as per local
G1: Rash covers <10% body	240mg.	policiese.g. anti-histamines, topical steroids
surface area	If persists >1-2 weeks despite	•
G2: Rash covers 10-30% body surface area	symptomatic treatment or recurs:	If persists >1-2 weeks or recurs:
	Delay nivolumab treatment	Consider skin biopsy.
	Restart nivolumab at 240mg if/when symptoms improve If steroids given, patient must have been weaned to ≤10mg per	Consider steroid treatment as per local policy (recommended dose 0.5mg to 1mg/kg/day IV

Grade 3: Covering >30% body surface area; erythroderma Grade 4: Life-threatening consequences	day (or equivalent) before restarting treatment. Maximum permitted delay 4 weeks. For grade 3: Delay nivolumab treatment. Restart nivolumab at 240mg if/when symptoms resolve. If steroids given, patient must have been weaned to ≤10mg per day (or equivalent) before restarting treatment. Maximum permitted delay 4 weeks. For grade 4: Permanently discontinue nivolumab treatment.	methylprednisolone equivalent dose of oral steroids). If worsens: treat as G3-4. Consider skin biopsy. Dermatology referral recommended. Steroid treatment as per local policy (recommended dose 1-2mg/kg/day IV methylprednisolone or equivalent dose of oral steroids). Prophylactic antibiotics against opportunistic infections.
Stevens-Johnson syndrome (SJS) or toxic epidermal necrolysis (TEN)	Permanently discontinue treatment.	Refer to specialist unit for assessment and treatment.

